6.5. Prior and Concomitant Medication

Prior medications and concomitant medications will be coded using the WHO Drug Dictionary March 2017 version and summarized by WHO drug class and WHO drug term by dose level and treatment group in the Phase 1 FAS population and by tumor type and treatment group in the Phase 2 FAS population. Results will be summarized as number and percentage of subjects with prior and concomitant medications by PT and WHO drug class.

7. EFFICACY

Sample data displays are provided in a separate document.

7.1. General Considerations

The primary efficacy endpoint for this study is ORR per RECIST v1.1 assessed in the Phase 2 response evaluable population. Secondary efficacy endpoints of this study include ORR, DOR, duration of disease control, disease control rate, and PFS by investigator assessment based on RECIST v1.1 and mRECIST as well as OS assessed at 1 year, 2 years, and EOS.

7.2. Efficacy Hypotheses

Each Simon 2-stage design will test the null hypothesis that the true ORR is less than or equal to the clinically insignificant response rate $p_0\%$ against the alternative hypothesis that the true ORR is equal to the target rate of $p_1\%$. For each Simon 2-stage design, the value for p_0 is determined by a historical response rate. The same values for p_0 and p_1 will be used for alternative dosing sequences in the same tumor type and treatment combination. For example, the gastric cohorts in Treatment Groups F, G, and H will all use the same value for p_0 and p_1 .

7.3. Analysis of the Efficacy Parameter

7.3.1. Response Criteria

Overall disease status will be categorized using RECIST v1.1. Subjects will have their overall response evaluated as CR, PR, SD, PD, or NE at each postbaseline radiological assessment based on changes in target lesions, nontarget lesions, and appearance of new lesions.

7.3.2. Objective Response Rate and Best Overall Response

7.3.2.1. Confirmed ORR and Confirmed BOR by RECIST v1.1

Per RECIST v1.1, in nonrandomized trials where response is the primary endpoint, confirmation of PR and CR is required to ensure responses are not the result of measurement error. Therefore, a subject is defined as a confirmed objective responder if the subject has an overall response of CR or PR at any postbaseline visit that is confirmed at a subsequent timepoint at least 4 weeks later, before the first occurrence of PD. Confirmed objective responders will be assessed based on RECIST v1.1.

Confirmed ORR is defined as the proportion of subjects with confirmed overall responses. Confirmed ORR will be estimated with 95% CIs. Confidence intervals will be based on the method for Simon 2-stage CIs of response rates outlined in Koyama and Chen (2008).

Confirmed ORR will be summarized by treatment group and tumor type as primary endpoint for the Phase 2 response evaluable population.

In general, confirmed BOR is the best response recorded postbaseline before and including the first PD, in the order of CR, PR, SD, PD and NE, in which CR and PR must be confirmed at a subsequent timepoint at least 4 weeks after the CR or PR is observed. Responses of CR, PR, or

SD after the first assessment of PD will not be considered. In the case of SD, measurements must meet the SD criteria at least once after the date of first dose at a minimum interval of 49 days. Subjects that fail to meet this criterion will have confirmed BOR of PD if the next available assessment indicates PD or NE if there is no additional assessment available.

Under RECIST v1.1, if radiologic imaging shows CR or PR, a tumor assessment should be repeated at a minimum of 4 weeks to confirm the response in order to claim the CR or PR as the confirmed BOR. If there is no second CR or PR tumor assessment, the CR or PR will be unconfirmed. [Table 4](#) lists the scenarios of responses that can occur after an unconfirmed CR or PR and provides a rule for determining the confirmed BOR in each scenario. A sensitivity analysis for the ORR, in which BOR is determined using unconfirmed PR and CR, is detailed in Section [7.3.2.2](#).

For determination of confirmed BOR, confirmatory scans with a response of NE will be subsequently followed by another scan at a minimum of 4 weeks. For example, in the case of PR at the first timepoint followed by NE at a subsequent timepoint, if a third scan shows a PR, then the confirmed BOR will be PR. There will be no third confirmatory scans performed for a loss of response. For example, if a response of PR at the first timepoint is followed by a response of SD or PD at a subsequent timepoint, the confirmed BOR will be determined using the rules in [Table 4](#).

Table 4: Derivation of Confirmed Best Overall Response

Overall Response at First Timepoint	Overall Response at Subsequent Timepoint	Confirmed Best Overall Response
CR	CR	CR
CR	PR	SD, PD, or PR ^a
CR	SD	SD, ^a provided minimum criteria for SD duration are met; otherwise, PD
CR	PD	SD, ^a provided minimum criteria for SD duration are met; otherwise, PD
CR	NE	SD, ^a provided minimum criteria for SD duration are met; otherwise NE
PR	CR	PR
PR	PR	PR
PR	SD	SD
PR	PD	SD provided minimum criteria for SD duration are met; otherwise, PD
PR	NE	SD, ^a provided minimum criteria for SD duration are met; otherwise NE
NE	NE	NE

^a If a CR is truly met at the first timepoint, then any disease seen at a subsequent timepoint, even disease meeting PR criteria relative to baseline, makes the disease PD at that point (since disease must have reappeared after CR). Confirmed BOR would depend on whether the minimum duration for SD was met. However, sometimes CR may be claimed when subsequent scans suggest small lesions were likely still present and in fact the subject had a PR, not a CR, at the first timepoint. Under these circumstances, the original CR should be changed to a PR, and the confirmed BOR is PR.

For subjects with measurable disease at baseline, the RECIST v1.1 assessment criteria presented in [Table 5](#) can be used to determine the overall disease status at a given timepoint based on the target lesion, nontarget lesion, and new lesion assessment.

Table 5: RECIST Evaluation Criteria for Overall Response: Measurable Disease at Baseline

Target Lesions	Nontarget Lesions	New Lesions	Overall Response
CR	CR	No	CR
CR	Non-CR/non-PD	No	PR
CR	NE	No	PR
PR	Non-PD or NE	No	PR
SD	Non-PD or NE	No	SD
Not all evaluated	Non-PD	No	NE
PD	Any	Yes or No	PD
Any	PD	Yes or No	PD
Any	Any	Yes	PD

7.3.2.1.1. Subgroup Analyses for Confirmed Best Overall Response Under RECIST v 1.1 in Phase 2

Subgroups will be formed based on the following subject characteristics and baseline variables for Phase 2 response evaluable subjects whose data are available:

- PD-L1 expression within tumor type: high, negative/low, unknown
- Number of prior therapies for advanced and metastatic disease within tumor type
- Subjects with > 1 postbaseline scan within tumor type
- Tumor-type disease characteristics for RCC and urothelial carcinoma

7.3.2.2. Unconfirmed ORR and Unconfirmed BOR by RECIST v1.1 – Sensitivity and Supportive Analyses for Confirmed ORR and Confirmed BOR by RECIST v1.1

A sensitivity analysis for the ORR assessed under RECIST v1.1 will be performed using unconfirmed CRs and PRs. The unconfirmed BOR is defined as the best response recorded postbaseline before and including the first PD, in the order of CR, PR, SD, PD, and NE. For this definition, responses of CR and PR do not need to be confirmed at a subsequent timepoint. In the case of SD, measurements must meet the SD criteria at least once after the date of first dose at a minimum interval of 49 (56-7) days. Subjects that fail to meet this criterion will have BOR of PD if the next available assessment indicates PD or NE if there is no additional assessment available.

Unconfirmed ORR will be summarized by treatment group and tumor type as a sensitivity analysis for the primary endpoint ORR for the Phase 2 response evaluable population and as a sensitivity analysis for the secondary endpoint ORR for the Phase 1 response evaluable population.

7.3.2.2.1. Subgroup Analyses for Unconfirmed Best Overall Response by RECIST v 1.1 in Phase 1

For the sensitivity analysis for unconfirmed BOR, subgroups will be formed based on subjects' prior treatment with an anti-PD-1/PD-L1 therapy within their tumor type (Yes/No) for Phase 1 response evaluable subjects and whose data are available.

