5.6.3. Prohibited Medications

Medications or vaccinations specifically prohibited in the exclusion criteria (see Section 3.2) are not allowed during the study. If there is a clinical indication for one of these medications or vaccinations specifically prohibited during the study, discontinuation from study treatment may be required. The investigator should discuss any questions regarding this with the medical monitor. The final decision on any supportive therapy or vaccination rests with the investigator and/or the subject's primary physician. However, the decision to continue the subject on study treatment requires the mutual agreement of the investigator, the sponsor, and the subject.

Subjects are prohibited from receiving the following therapies during the screening and treatment periods of this study:

- Any anticancer medications, including chemotherapy or biologic therapy other than study treatment.

- Any immunological-based treatment for any reason from screening through the safety follow-up visit is prohibited.

Note: Completed adjuvant therapy (eg, vaccines) with medical monitor approval, inhaled or topical steroids, systemic steroids at doses \leq 10 mg/day prednisone or equivalents, and immune suppressants are allowed for treatment for immune toxicities as described in Section 5.4.7 and [Appendix B](#), or as prophylaxis for contrast allergy for imaging procedures.

Note: Allergy shots may be permitted after consultation with the medical monitor.

- Investigational agents other than study treatment. Use of such medications from screening through the safety follow-up visit is prohibited.

- Concomitant radiation therapy.

Note: Radiation therapy to a symptomatic solitary lesion or to the brain may be considered on an exceptional case-by-case basis after consultation with the medical monitor. The subject must have clear measurable disease outside the radiated field. Administration of palliative radiation therapy will be considered clinical progression for the purposes of determining PFS.

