^k If scan was obtained within 4 weeks before the date of treatment discontinuation, then a scan at treatment discontinuation (EOT) is not mandatory. For subjects who discontinue study therapy without confirmed disease progression, a radiologic evaluation should be repeated at the time of treatment discontinuation (ie, date of discontinuation \pm 4 week window).

Table 13: Schedule of Laboratory Assessments

Visit Day (Range)	Protocol Section	Timing of Assessment	Screening	Treatment								Post-Treatment			
				C1		C2	C4	C6		C7	Every 4th Cycle (C8, C12)	All Other Cycles	EOT	Safety Follow-Up Visit 1	Safety Follow-Up Visit 2
				D1	D8	D1	D1	D1	D8	D1	D1	D1			
Evaluation/Window		Day -28 to -1		± 1 day	± 3 days	± 3 days	± 3 days	30 days (+ 7 days)	60 days (+ 7 days)						
Local laboratory tests^a															
Comprehensive serum chemistries ^b	7.6.5	N/A	X ^c	X ^d	X	X	X	X		X	X	X	X	X	X
Hematology with differential	7.6.5	N/A	X ^c	X ^d	X	X	X	X		X	X	X	X	X	X
Coagulation panel ^e	7.6.5	N/A	X ^c												
Urinalysis	7.6.5	N/A	X ^c												
Endocrine function tests	7.6.5	N/A	X ^c				X				X		X	X	
Hepatitis B and C	7.6.5.2	N/A	X												
Serum pregnancy test (childbearing females only) ^f	7.6.5.1	N/A	X										X		
Urine pregnancy test (childbearing females only)	7.6.5.1	N/A													

^a All safety laboratory assessments will be performed locally.

^b If liver chemistry tests increase in grade from baseline or are ≥ Grade 3, then liver chemistry monitoring should increase to once per week until resolved to baseline or ≤ Grade 1. Liver chemistry does not need to be monitored once per week indefinitely for persistent low grade abnormalities. Appropriate liver chemistry monitoring intervals should be discussed with the medical monitor for these circumstances.

^c Screening laboratory tests must be performed within 7 days of Cycle 1 Day 1. If performed more than 7 days before Cycle 1 Day 1, then the tests must be repeated and eligibility confirmed before study treatment administration on Cycle 1 Day 1.

^d Only required to be performed at Cycle 1 Day 1 if the screening assessment was not performed within 7 days.

^e Subjects on anticoagulation treatment should have parameters monitored throughout the study as clinically indicated.

^f A serum pregnancy test will be required for all women of childbearing potential during screening and must be within 72 hours before the first dose of study treatment.

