7.3.3.1. Duration of Response by RECIST v1.1

Under RECIST v1.1, for unconfirmed objective responders, DOR is defined as the time from the first overall response contributing to an unconfirmed objective response (CR or PR) to the earlier of the subject's death from any cause or first assessment of PD.

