7.3.4. Duration of Disease Control and Disease Control Rate

Duration of disease control (CR, PR, and SD) is defined as the time from the first report of SD or better until disease progression or death from any cause, if occurring sooner than progression, as determined by investigator assessment of radiographic disease per RECIST v1.1 and mRECIST. Note that the criteria for the assessment of PD in duration of disease control are the same with ORR, which are presented in Section [7.3.2.3](#).

The duration of disease control will be estimated with 95% CIs overall and by treatment group. Confidence intervals will be calculated based on the exact method for binomial distributions. Swim plots for duration of disease control will be generated separately for RECIST v1.1 and mRECIST criteria.

Disease control rate, defined as the proportion of subjects who have disease control (CR + PR + SD), as per RECIST v1.1 and mRECIST will be summarized. For the determination of DCR, response of CR and PR do not need to be confirmed at a subsequent timepoint. In the case of SD, measurements must meet the SD criteria at least after the date of first dose at a minimum of 49 days. Subjects who fail to meet this criterion will have confirmed BOR of PD if the next available assessment indicated PD or NE if there is no additional assessment available. Disease control rate will be estimated with 95% CIs.

Duration of disease control and DCR as assessed per RECIST v1.1 and mRECIST will be summarized by treatment group and dose level for the Phase 1 response evaluable population and by treatment group and tumor type for the Phase 2 response evaluable population.

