7.3.5. Largest Percentage Reduction in Sum of Diameters of Target Lesions

For each subject in the FAS population with target lesions at baseline, target lesion sizes will be measured by sum of diameters. The best percentage change from baseline, defined as the largest decrease in target lesion size for each subject, will be summarized descriptively, and a waterfall plot of the best percentage change will be generated.

Per RECIST criteria, target lesions considered "too small to measure" will be assigned a default value of 5 mm for purposes of this analysis. Likewise, target lesions identified as "not present" at postbaseline assessments will be assigned 0 mm for this analysis. In the event a target lesion is unaccounted for in a particular postbaseline timepoint (ie, assessment missing or NE), then the overall sum of diameters for target lesions will not be evaluable for that postbaseline timepoint.

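### The SAP's best-response rules stop only at radiological PD, so a response seen after permitted palliative radiotherapy would count in the Phase 1 ORR, DCR and waterfall displays

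*SAP*

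**What the plan says.** **Response rules (SAP).** For the confirmed analysis, 7.3.2.1 says that "confirmed BOR is the best response recorded postbaseline before and including the first PD", and a responder's CR or PR must be "confirmed at a subsequent timepoint at least 4 weeks later, before the first occurrence of PD". For the sensitivity analysis, 7.3.2.2 says: "The unconfirmed BOR is defined as the best response recorded postbaseline before and including the first PD". Under 7.3.1, PD is a category assigned at a post-baseline radiological assessment. For disease control, 7.3.4 says: "For the determination of DCR, response of CR and PR do not need to be confirmed at a subsequent timepoint"; it sets a minimum duration for SD but no cut-off for other therapy. The waterfall variable in 7.3.5 is described as: "The best percentage change from baseline, defined as the largest decrease in target lesion size for each subject". No end point is given for it.

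**Time-to-event rules (SAP).** Table 7 governs PFS censoring, and 7.3.3 applies the same algorithm to DOR. It has a row for the start of new anticancer treatment, which censors at the latest valid scan. It has no row for radiotherapy.

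**Other therapy on study (Protocol).** Section 5.6.3 prohibits other anticancer drugs and concomitant radiotherapy, with one exception: "Radiation therapy to a symptomatic solitary lesion or to the brain may be considered on an exceptional case-by-case basis". The medical monitor must be consulted, and there must be measurable disease outside the field. The same note counts palliative radiotherapy as clinical progression, but only in determining PFS. Section 7.7.1.1.2 ends imaging when new anticancer treatment starts, and 6.4 then treats the subject as having completed the study. Table 12, footnote k, says that for subjects stopping without confirmed progression "a radiologic evaluation should be repeated at the time of treatment discontinuation", within 4 weeks either side of that date.

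**The concern.** The efficacy objective concerns INCAGN01949 given with immune therapies. A best-response rule that runs to first radiological PD, whatever else is given before then, credits the combination with shrinkage that local treatment may have produced. The protocol accepts for PFS that palliative radiotherapy ends the period in which the subject is doing well on study treatment, but the response endpoints do not follow. One subject can then be a progressor for PFS and a later responder for ORR and DCR.

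If this happens, it can only add responders, disease control and apparent shrinkage. The affected displays are still to be produced. Protocol Section 9 limits the analysis to Phase 1, and SAP Appendix A reports best response (Tables 2.1.1.1 and 2.1.1.2) and the waterfall plot (Figure 4.1.4.1) by treatment group and dose, where cells are small.

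**Working it through.** **1. The plan's own figure.** Both documents use the same Simon design for the anti-PD-1/L1 cohorts: stop with 2 or fewer responses in 20, with p0 = 10% and p1 = 25% (Protocol Table 21, SAP Table 2). The probability of early termination is P(X ≤ 2), with X binomial on n = 20:

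- p = 0.10: 0.9^20 + 20(0.1)(0.9^19) + 190(0.1^2)(0.9^18) = 0.1216 + 0.2702 + 0.2852 = 0.6769 (rounded from the unrounded sum).
- p = 0.25: 0.75^20 + 20(0.25)(0.75^19) + 190(0.25^2)(0.75^18) = 0.0032 + 0.0211 + 0.0670 = 0.0913.

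Both match SAP Table 11. Exact enumeration of the full 2/20, 8/50 design gives a Type I error of 0.0482 and a power of 0.8535, consistent with the stated 0.05 and 85%. No figure in the documents is wrong on this point.

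**2. A subject given palliative radiotherapy before radiological PD.**

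| Endpoint | Governing text | Effect of the radiotherapy |
|---|---|---|
| PFS | Protocol 5.6.3 | Counts as progression |
| PFS | SAP Table 7 | No row; follow-up simply continues |
| Confirmed and unconfirmed ORR | SAP 7.3.2.1, 7.3.2.2 | None; later scans count until radiological PD |
| DCR | SAP 7.3.4 | None stated |
| Best target-lesion change | SAP 7.3.5 | None; no end point at all |
| DOR | SAP 7.3.3 through Table 7 | None; a response first seen later starts a duration |

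Clinical progression is not a radiological category, so under 7.3.1 it does not act as PD in the best-response rule. The requirement for measurable disease outside the field does not take an irradiated target lesion out of the sum of diameters. At entry the protocol does deal with this problem: a previously irradiated lesion is not measurable unless it has progressed (3.1, criterion 7) and should not be chosen as a target (7.7.1.1.1). There is no on-study counterpart.

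**3. A subject who starts new anticancer therapy before radiological PD.** Planned imaging stops. The scans that could still exist are an end-of-treatment scan up to 4 weeks after discontinuation, or one taken off schedule. A response first seen on the end-of-treatment scan cannot enter confirmed ORR through planned imaging, because confirmation needs a second scan at least 4 weeks later and none is scheduled. It could enter unconfirmed ORR, DCR and best change, or confirm an earlier response. Table 7 censors PFS and DOR, but it does not say that the scan used as the censoring date must precede the new therapy. Its row for missed assessments does specify a scan before death.

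**4. Size.** One misattributed responder changes ORR by 1/n. Cells of 3, 6 and 9 come from the 3 + 3 + 3 rule (Protocol 4.1.1), and 52 is total enrollment:

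- 1/3 = 33.3, 1/6 = 16.7 and 1/9 = 11.1 percentage points
- 1/52 = 1.9 percentage points

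The documents give no frequency. Taking 0 to 2 subjects in 52 as an assumption, the overall shift is 0 to 2/52 = 3.8 points.

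**The case against.** The strongest case on the other side is that this is rare and mostly handled. Radiotherapy is prohibited apart from an exception that is case by case, needs consultation, and requires measurable disease elsewhere. Overall response also depends on all target, nontarget and new lesions, so shrinking one irradiated lesion need not produce a PR. The protocol limits its progression rule to PFS, and carrying it over to response is arguably a preference. Section 5.6.3 also says that subjects who need the listed treatments should leave the study. The argument from rarity stands and limits the weight of the point. The rest does not close the gap. Requiring disease outside the field makes sense only if the subject goes on being assessed, and no rule says how the later scans are used.

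It might also be said that radiotherapy is itself new anticancer treatment, so that Table 7 and the imaging stop already cover it. Protocol 5.6.3 lists it separately from anticancer drugs. On that reading Table 7 would also censor a subject whom the protocol counts as progressed, so the two would still disagree.

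A reader might infer that responses to any later anticancer drug count freely in ORR, DCR and DOR. The documents do not support this. Such drugs are prohibited on treatment, imaging ends when they start, the subject then completes the study, and DOR takes its censoring from Table 7. Only the residual scans in step 3 remain.

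**Conclusion.** The point holds for palliative radiotherapy, and as a residual gap for new anticancer therapy. Followed as written, the SAP would count a response seen after radiotherapy in ORR, DCR and the waterfall plot for a subject whom the protocol treats as progressed for PFS. SAP Table 7 does not carry out the protocol's PFS rule either.

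The size rests on a frequency that the documents do not give and that may be zero. It also assumes that response-evaluable cells are about the size of the escalation cohorts. Under those conditions one subject moves ORR by 33, 17 or 11 points in a cell of 3, 6 or 9, and by 1.9 points in 52. These figures show how sensitive small cells are; they do not show that the event is likely.

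A reader might go further and infer that the Simon decisions are biased, or might measure the shift against the 15-point gap between 10% and 25%. Neither follows. Phase 2 will not open, that contrast belongs to PD-1/L1 refractory subjects, and Phase 1 ORR is a secondary, descriptive result in a mixed population with no formal test. This is a minor correction, worth making because it is cheap and the error, if it occurs, favours the combination.

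**What to change.** - **SAP 7.3.2.1, 7.3.2.2, 7.3.4 and 7.3.5:** use only assessments up to the earliest of first PD, start of new anticancer therapy, or palliative radiotherapy. Scans that confirm a CR or PR must meet the same limit. List later scans without using them. Keep the subject in the denominator with the best response reached by then.
- **SAP Table 7:** add a palliative radiotherapy row that agrees with Protocol 5.6.3, with its date stated. Specify that censoring for new therapy uses the last valid scan before that therapy. The table also serves DOR, so both changes carry over to it; say so in 7.3.3.

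The cost is a sentence in each of four sections, two edits to one table, and one date cut in the response dataset. Concomitant treatments and procedures are already recorded in the eCRF (Protocol 5.6, 7.4), and new anticancer therapy is reviewed under 7.5. The downside is that a genuine response outside the irradiated field, first seen after radiotherapy, would not count, so reported ORR could be slightly lower. Listing the later scans keeps such a case visible.
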